1.2.7.1 Data Analysis

For each patient an attempt to fit Equation (A) to each data set for which more than one data point is available. Curve fitting will be performed using SigmaPlot (Systat Software), or by using the Solver routine in an Excel spreadsheet. We will extract parameters g and d with their associated Student's t and P values¹⁹. Data will be analyzed in Excel (Microsoft) and in SigmaPlot 9.0. Linear regressions to evaluate the relationship between the growth rate constant, g , or other parameters will be implemented using the polynomial linear routine of SigmaPlot 9.0. Sample comparisons were performed by Student's t -test, using SigmaStat 3.5 (Systat Software), with P set at 0.05 for significance.¹⁶

2 ELIGIBILITY ASSESSMENT AND ENROLLMENT

2.1 ELIGIBILITY CRITERIA

2.1.1 Inclusion Criteria

2.1.1.1 Histopathological documentation of prostate cancer confirmed in either the Laboratory of Pathology at the National Institutes of Health (NIH) Clinical Center, Walter Reed National Military Medical Center, MSKCC, DFCI or BIDMC prior to enrollment. If no pathologic specimen is available, patients may enroll with a pathologist's report showing a histologic diagnosis of prostate cancer and a clinical course consistent with the disease.

2.1.1.2 Biochemical progression after definitive radiation or surgery defined as follows:

- For patients following definitive radiation therapy: a rise in PSA of ≥ 2 ng/mL above the nadir (per RTOG-ASTRO consensus criteria).
- For patients following radical prostatectomy: rising PSA after surgical procedure. (Patients must have a PSA ≥ 0.8 ng/ml)

2.1.1.3 ECOG performance status of 0–1 (Karnofsky $\geq 80\%$, see **APPENDIX A**).

2.1.1.4 Patients must have a PSA doubling time of 5–15 months.

2.1.1.5 Patients must have a rising PSA as confirmed by 3 values done at least 1 week apart and over no less than 1 month.

- 2.1.1.6 Recovery from acute toxicity related to prior therapy, including surgery and radiation, or no toxicity \geq grade 2.
- 2.1.1.7 Negative CT scan/MRI and bone scan for metastatic prostate cancer.
- 2.1.1.8 Hematological eligibility parameters (within 16 days before starting therapy; see **APPENDIX D**):
 - Granulocyte count $\geq 1000/\text{mm}^3$
 - Platelet count $\geq 100\,000/\text{mm}^3$
 - Hgb $\geq 10\text{ g/dL}$
- 2.1.1.9 Biochemical eligibility parameters (within 16 days before starting therapy):
 - Hepatic function: bilirubin $\leq 1.5\text{ mg/dL}$ (OR in patients with Gilbert's syndrome, a total bilirubin ≤ 3.0), AST and ALT ≤ 2.5 times upper limit of normal.
- 2.1.1.10 No other active malignancies within the past 36 months (with the exception of nonmelanoma skin cancers or carcinoma in situ of the bladder) or life-threatening illnesses, in the opinion of the investigator.
- 2.1.1.11 Willing to travel to the NIH, MSKCC, DFCI, BIDMC for follow-up visits.
- 2.1.1.12 18 years of age or older.
- 2.1.1.13 Able to understand and sign informed consent.
- 2.1.1.14 Baseline testosterone $\geq 100\text{ ng/dl}$
- 2.1.1.15 PSA $\leq 30\text{ ng/mL}$.
- 2.1.1.16 The effects PROSTVAC on the developing human fetus are unknown. For this reason, men must agree to use adequate contraception (hormonal or barrier method of birth control; abstinence) prior to study entry, for the duration of study therapy and at least one month post therapy. Should a woman become pregnant or suspect she is pregnant while her partner is participating in this study, she should inform her treating physician immediately.

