1.2 BACKGROUND AND RATIONALE

1.2.1 Rationale for conducting the study in biochemically recurrent prostate cancer patients

Prostate cancer is the most common malignancy among men in the United States with an estimated 220,800 new diagnoses and over 27,540 deaths in 2015.³ Although surgery or radiation can cure the majority of newly diagnosed patients, 20-40% are likely to have recurrent disease manifested as a rising PSA despite negative conventional imaging studies (CT and technetium-99m (Tc-99m) Bone Scan) used to detect metastasis.^{4,5} This stage of disease is often referred to as biochemically recurrent prostate cancer.

Despite the fact that nearly 90,000 men who are diagnosed each year with prostate cancer will ultimately develop biochemically recurrent prostate cancer there is no clear standard of care for these patients.⁶ Treatments range from active surveillance to intermittent or continuous androgen deprivation therapy (ADT) and in some cases salvage radiation or surgery. Ideal effective non-hormonal treatment strategies in this population would avoid or delay the onset of metastatic castration resistant prostate cancer (mCRPC). There are two significant obstacles to developing therapies in this asymptomatic population; (1) therapies need to have minimal toxicity (2) conventional clinical endpoints (metastatic progression and overall survival) can take 5-10 years.

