2.1.2 Exclusion Criteria

- 2.1.2.1 Immunocompromised status due to:

- Human immunodeficiency virus (HIV) positivity.
- Active autoimmune diseases such as Addison's disease, Hashimoto's thyroiditis, systemic lupus erythematosus, Sjogren syndrome, scleroderma, myasthenia gravis, Goodpasture syndrome or active Grave's disease. Patients with a history of autoimmunity that has not required systemic immunosuppressive therapy or does not threaten vital organ function including CNS, heart, lungs, kidneys, skin, and GI tract will be allowed.
- Other immunodeficiency diseases
- Splenectomy

- 2.1.2.2 Chronic administration (defined as daily or every other day for continued use > 14 days) of corticosteroids deemed systemic by investigator within 28 days before the first planned dose of PROSTVAC. Use of inhaled steroids, nasal sprays, intra-articular injections and topical creams for small body areas is allowed.
- 2.1.2.3 Serious intercurrent medical illness that, in the judgment of the investigator, would interfere with patient's ability to carry out the treatment program.
- 2.1.2.4 Other medications used for urinary symptoms including 5-alpha reductase inhibitors (finasteride and dutasteride) and alternative medications known to alter PSA (eg phytoestrogens and saw palmetto)
- 2.1.2.5 History of prior chemotherapy
- 2.1.2.6 History of prior immunotherapy within the last 3 years
- 2.1.2.7 Major surgery within 4 weeks prior to enrollment (Day 1 visit).
- 2.1.2.8 History of allergic reactions attributed to compounds of similar chemical or biologic composition to poxviral vaccines (e.g., vaccinia vaccine)
- 2.1.2.9 Known allergy to eggs, egg products, aminoglycoside antibiotics (for example, gentamicin or tobramycin).
- 2.1.2.10 History of atopic dermatitis or active skin condition (acute, chronic, exfoliative) that disrupts the epidermis
- 2.1.2.11 Previous serious adverse reactions to smallpox vaccination
- 2.1.2.12 Unable to avoid close contact or household contact with the following high-risk individuals for three weeks after the Day 1 vaccination: (a) children \leq 3 years of age, (b) pregnant or nursing women, (c) individuals with prior or concurrent extensive eczema or other eczemoid skin disorders, or (d) immunocompromised individuals, such as those with HIV.
- 2.1.2.13 Receipt of an investigational agent within 28 days (or 56 days for an antibody-based therapy) before the first planned dose of study drugs.
- 2.1.2.14 Patients who test positive for HBV or HCV

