3 STUDY IMPLEMENTATION

3.1 STUDY DESIGN

- This is a randomized trial of PROSTVAC for 6 months vs. surveillance for 6 months followed by PROSTVAC for 6 months in patients with nmCSPC prostate cancer. 72 evaluable patients will be enrolled with an accrual ceiling of 110 patients
- PROSTVAC will be administered identical to the Phase III dosing with vaccine given week 1 (vaccinia-PROSTVAC, 2x10⁸ infectious units subcutaneously) and then fowlpox-vaccine (1x10⁹ infectious units subcutaneously) on weeks 3 and 5 followed by monthly fowlpox-vaccine (1x10⁹ infectious units subcutaneously) for a total of 5 months (including vaccinia, vaccine is administered over 6 months).
- The primary endpoint of this trial will be to determine if PROSTVAC can decrease tumor growth rate as measured by PSA rise after 6 months compared to a group getting surveillance alone. This time frame should be sufficient to evaluate immune effect on the re-growth rate given that the ECOG 9802 analysis demonstrated a significant change in tumor growth rate after starting PROSTVAC.
- Secondary endpoints include observing the effects of vaccine on PSA growth rate when prostvac is initiated after 6 months of surveillance, immune response evaluation will include CD4 cells, CD 8 cells, PSA-specific T-cells, natural killer cells, Regulatory T-cells, Regulatory T-cell function, cytokines, naïve thymic emigrants, associate immunologic outcomes with PSA responses/changes in growth rates.
- For patients who have a PSA doubling time greater than 5 months (measured over the previous 6 months of treatment), they may receive maintenance vaccine every 3 months for an additional year. For patients who are on-study at the time of this amendment, they will be given an option to receive 1 year of vaccine maintenance (4 doses, administered every 3 months).
- When possible, patients will be followed for TTP beyond the treatment period.

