3.6 CONCURRENT THERAPIES

Concurrent hormonal therapy will not be allowed. Concurrent anticancer treatment with chemotherapy, systemic glucocorticoids (topical and inhaled steroids allowed), radiation therapy, major surgical procedures for prostate cancer, and nonprotocol-related immunotherapy will not be permitted.

Concurrent systemic corticosteroid use (daily or every other day for continued use > 14 days) will also not be allowed.

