8 STATISTICAL CONSIDERATIONS

The primary endpoint of this trial is to determine if prostvac can slow the growth rate of prostate cancer relative to a group of patients on surveillance. With 36 evaluable patients with a growth rate value from 0 to 6 months on the Prostvac arm and 36 evaluable patients on the surveillance arm (72 total patients) there would be adequate patients to have 80% power to test for a difference between the two arms of a change in growth rate from baseline equal to 2/3 SD of the change (0.67 SD effect size) using a 0.05 significance level two-tailed two group t-test. In practice, if the distributions of the growth rate constants are not normally distributed ($p < 0.05$ by a Shapiro-Wilks test), then a Wilcoxon rank sum test may be used instead of a two-sample t-test. In order to allow for a small number of inevaluable subjects as well as to accommodate screen failures, the accrual ceiling will be set at 110. (It is estimated that it will take 4 years to complete accrual to this trial.)

Secondary Endpoints

In addition, using the surveillance arm, two related endpoints will be explored, both the actual magnitude of the change in the growth rate parameter as well as the fraction who exhibit a substantial, 50% decline in the growth rate as a result of treatment. For the 36 patients who will be enrolled on the surveillance arm, the growth rate determined at 12 months (after 6 months of vaccine) will be subtracted from that obtained at 6 months (after surveillance) to determine the actual change in the growth rate for receiving vaccine after 6 months of surveillance. With 36 patients, there is 83% power to detect a difference in the values at the two time points equal to 1/2 of the SD of the change (.50 effect size) assuming that a two tailed 0.05 alpha level paired t-test is used.

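### No limit on recent ADT at entry and no use of testosterone in section 8: the uncontrolled Arm B before-after analyses can count testosterone recovery as vaccine slowing

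*Combined protocol and SAP*

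**What the plan says.** **Entry.** The only androgen condition is in 2.1.1.14, "Baseline testosterone", with a floor of 100 ng/dL. Other prior treatments carry explicit limits in 2.1.2: "History of prior chemotherapy" at any time, "History of prior immunotherapy within the last 3 years", chronic systemic corticosteroids (28 days) and investigational agents (28 or 56 days). Section 2.1.2.4 also excludes 5-alpha reductase inhibitors and "alternative medications known to alter PSA (eg phytoestrogens and saw palmetto"), so the protocol recognises that medication can distort PSA. Prior ADT appears in none of these lists.

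**On study.** Section 3.6 states "Concurrent hormonal therapy will not be allowed", and section 5.1 bars concomitant secondary hormonal treatment. Neither addresses past use.

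**Population.** Section 1.2.1: "Treatments range from active surveillance to intermittent or continuous androgen deprivation therapy (ADT"). Section 3.1 places the trial "in patients with nmCSPC prostate cancer", that is, non-metastatic castration-sensitive disease.

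**Data and analysis.** Both Appendix C calendars put testosterone on the same row as serum PSA, so it is drawn whenever PSA is. Neither 1.2.7 nor section 8 uses it, and 2.3.2 states no stratification factor. The primary test in section 8 is a concurrent randomised comparison over months 0-6. Two secondary analyses use Arm B alone. One subtracts growth rates at 6 and 12 months "to determine the actual change in the growth rate for receiving vaccine after 6 months of surveillance"; the other counts men whose growth rate falls by 50% after vaccine starts.

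**The concern.** In castration-sensitive disease, PSA can climb faster than tumour growth alone while testosterone recovers after ADT, then slow when testosterone levels off. One value above 100 ng/dL does not show that recovery is complete. In Arm B the earlier window is surveillance and the later one is vaccine. A man still recovering during surveillance therefore contributes a fall in growth rate that the before-after analysis credits to the vaccine, and no concurrent untreated group removes it.

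At stake is the first listed secondary objective, the effect of vaccine on PSA growth rate when started after six months of surveillance, together with the 50%-decline fraction.

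**Working it through.** **1. The plan's own figures reproduce.**
- Primary: two-sample t-test, 36 per arm, 0.67 SD, two-sided 0.05. The noncentral t gives 80.05% (stated 80%).
- Arm B paired t-test: n = 36, 0.50 SD. Power is 83.1% (stated 83%).
- Arm B 50%-decline test: exact binomial, n = 36, null 30%, alternative 50%, one-sided 0.05. The smallest rejection count with error at most 0.05 is 16, since P(X ≥ 15) = 9.2% and P(X ≥ 16) = 4.7% at p = 0.30. Power at p = 0.50 is 79.7% (stated 79%).

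None of these figures is wrong.

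**2. The entry window admits the artefact.** Growth rate is g = ln 2 / doubling time. A doubling time of 5 months gives 0.1386 per month, and 10 months gives 0.0693. Both lie within the 5-15 month range of 2.1.1.4, and moving from one to the other is a 50% fall, the event that section 8 counts.

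**3. Effect on the 50%-decline test (assumed inputs).** Let r be the share of Arm B still recovering. Suppose every such man counts as a decline and the others meet the 30% null. The no-vaccine fraction is then p = r + (1 − r) × 0.30.

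| r (assumed) | p | Rise over 30% | P(X ≥ 16 of 36) |
|---|---|---|---|
| 0 | 30% | 0 points | 4.7% |
| 5% | 33.5% | 3.5 points | 11.4% |
| 10% | 37% | 7 points | 22.4% |
| 15% | 40.5% | 10.5 points | 37.4% |

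**4. Why these are upper bounds.** Take a 5-month doubling time during recovery and 10 months afterwards, with recovery ending at month m of surveillance. In units of the later rate, the mean rate over the six-month window is (2m + (6 − m)) / 6, and the apparent fall into the vaccine window is 1 − 6 / (6 + m).
- m = 2: 25%
- m = 3: 33%
- m = 4: 40%
- m = 6: 50%

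In this example only a recovery that fills the whole surveillance window reaches 50%. Wider contrasts within the 5-15 month range could reach it sooner.

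**5. Effect on the Arm B paired test.** This was simulated with 40,000 runs per setting, no vaccine effect, a share f of men recovering, and a spurious slowing of s SD in each. Over f = 10-30% and s = 0.5-2, the chance of a significant false slowing rises from 2.5% to between 5% and 74%; at f = 20%, s = 1 it is 19%. The range is wide because the documents give neither input.

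**6. Effect on the primary test.** With the same inputs in both arms and no vaccine effect, two-sided error stays at 4.9-5.3% and false slowing at 2.4-2.7% (nominal 2.5%). The cost is variance: the SD grows by √(1 + f(1 − f)s²), and power for the planned difference falls from 80% to 54-79%. At f = 20%, s = 1 the factor is √1.16 = 1.077 and power is about 74%.

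**The case against.** A reader might infer that the trial's main result could be a testosterone artefact. The documents do not support that: allocation is concurrent and 1:1, both arms meet the same entry rule, and step 6 shows no inflation of error.

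A reader might also take 11-37% as the expected error. Several facts count against this:
- The Arm B analyses are secondary and described as explorations. For the 50%-decline fraction, the stated practice is to report a 95% confidence interval.
- The documents give no ADT prevalence, recovery duration or PSA response to recovery. A man whose recovery ends before or early in surveillance contributes little.
- The testosterone floor is not the only guard. The 5-month lower limit on doubling time removes the steepest rises, and three rising values are required.
- Testosterone is scheduled throughout, so the artefact could be examined.

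All of this stands, and it limits the point to the Arm B analyses and the figures to upper bounds. It does not close the gap. The rising PSA need span only one month (2.1.1.5), and a 5-to-10-month change passes entry. A confidence interval around a shifted fraction is shifted too. Testosterone that no analysis uses corrects nothing.

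**Conclusion.** The concern holds for the two Arm B before-after analyses. Entry allows men whose testosterone is still recovering from ADT, those analyses have no concurrent control, and section 8 does not use the testosterone collected. If 5%, 10% or 15% of Arm B were recovering, the false-positive chance of the 16-of-36 rule would rise from 4.7% to at most about 11%, 22% or 37%. This assumes that every recovering man shows a full 50% fall and that the rest meet the 30% null; it is less if recovery ends early in surveillance. The shares are assumptions, and the documents do not show that any such man was enrolled.

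For the randomised primary comparison the consequence is limited to extra variance and possible chance imbalance among 72 men with no stated stratification.

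**What to change.** In section 8:
- Prespecify that both Arm B analyses are repeated excluding, or adjusting for, men whose testosterone rises materially from baseline to month 6. Fix the threshold before the data are examined. This change precedes the first Arm B vaccination, so selecting on it does not select on a vaccine effect.
- Tabulate testosterone change by arm.
- For the primary comparison, go no further than a descriptive table or adjustment for baseline testosterone. Excluding men on post-randomisation testosterone could disturb the randomised comparison.

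The cost is a few lines of text and one table, since the samples are already scheduled. Recording prior ADT and its stop date would help interpretation. Whether the entry criterion should change is for the sponsor and investigator.

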2.1.2 Exclusion Criteria

- 2.1.2.1 Immunocompromised status due to:

- Human immunodeficiency virus (HIV) positivity.
- Active autoimmune diseases such as Addison's disease, Hashimoto's thyroiditis, systemic lupus erythematosus, Sjogren syndrome, scleroderma, myasthenia gravis, Goodpasture syndrome or active Grave's disease. Patients with a history of autoimmunity that has not required systemic immunosuppressive therapy or does not threaten vital organ function including CNS, heart, lungs, kidneys, skin, and GI tract will be allowed.
- Other immunodeficiency diseases
- Splenectomy

- 2.1.2.2 Chronic administration (defined as daily or every other day for continued use > 14 days) of corticosteroids deemed systemic by investigator within 28 days before the first planned dose of PROSTVAC. Use of inhaled steroids, nasal sprays, intra-articular injections and topical creams for small body areas is allowed.
- 2.1.2.3 Serious intercurrent medical illness that, in the judgment of the investigator, would interfere with patient's ability to carry out the treatment program.
- 2.1.2.4 Other medications used for urinary symptoms including 5-alpha reductase inhibitors (finasteride and dutasteride) and alternative medications known to alter PSA (eg phytoestrogens and saw palmetto)
- 2.1.2.5 History of prior chemotherapy
- 2.1.2.6 History of prior immunotherapy within the last 3 years
- 2.1.2.7 Major surgery within 4 weeks prior to enrollment (Day 1 visit).
- 2.1.2.8 History of allergic reactions attributed to compounds of similar chemical or biologic composition to poxviral vaccines (e.g., vaccinia vaccine)
- 2.1.2.9 Known allergy to eggs, egg products, aminoglycoside antibiotics (for example, gentamicin or tobramycin).
- 2.1.2.10 History of atopic dermatitis or active skin condition (acute, chronic, exfoliative) that disrupts the epidermis
- 2.1.2.11 Previous serious adverse reactions to smallpox vaccination
- 2.1.2.12 Unable to avoid close contact or household contact with the following high-risk individuals for three weeks after the Day 1 vaccination: (a) children \leq 3 years of age, (b) pregnant or nursing women, (c) individuals with prior or concurrent extensive eczema or other eczemoid skin disorders, or (d) immunocompromised individuals, such as those with HIV.
- 2.1.2.13 Receipt of an investigational agent within 28 days (or 56 days for an antibody-based therapy) before the first planned dose of study drugs.
- 2.1.2.14 Patients who test positive for HBV or HCV
- 2.1.2.15 Uncontrolled hypertension (SBP>170/ DBP>105)

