- As a precaution, the CDC recommends that individuals with known cardiac disease (e.g., previous MI, angina, CHF, cardiomyopathy, stroke or TIA) or who have ≥ 3 known risk factors for cardiac disease (e.g., hypertension, hypercholesterolemia, diabetes, first degree relative with onset of cardiac complications prior to age 50, smoker), not receive routine, non-emergency, prophylactic vaccination with the licensed vaccinia vaccine while a possible causal relationship between vaccination and cardiac events is being evaluated.

Avoid exposure to the recombinant vaccinia vaccine, any contaminated dressings, or other infectious materials from patients, or the patient's inoculation site if you are pregnant or breast-feeding; have a history or presence of active eczema or atopic dermatitis; have acute, chronic or exfoliative skin conditions; or, are immunocompromised. More information on vaccinia precautions for healthcare workers can be obtained from

<http://www.cdc.gov/mmwr/preview/mmwrhtml/rr5010a1.htm#tab2> and

<http://www.cdc.gov/mmwr/PDF/rr/rr5207.pdf>.

The CDC is the only source of the licensed vaccinia vaccine. The CDC will provide vaccinia vaccine to protect laboratory and other healthcare personnel, whose occupations place them at risk of exposure to vaccinia and other closely related orthopoxviruses, including vaccinia recombinants. The vaccine should be administered under the supervision of a physician selected by the study institution. Revaccination is recommended every 10 years. For instructions on obtaining the licensed vaccinia vaccine, contact Drug Services, National Center for Infectious Diseases, CDC at [contact].

Recombinant Vaccinia Vaccine Patient Care Implications, Contraindications and Potential Complications

Patient Care Implications and Contraindications

Cover vaccination sites with a sterile dry dressing (e.g., Telfa pad). Instruct patients on proper hand-hygiene, sterile dressing care, bathing, laundering of clothing, etc. Treat patient bandages or dressings removed from the vaccination site as infectious waste and dispose in appropriate biohazard containers. Do not administer the recombinant vaccinia vaccine if the recipient, or for at least three weeks after vaccination, their close household contacts (close household contacts are those who share housing or have close physical contact):

- have active eczema or a history of eczema or atopic dermatitis, or Darier's disease.

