- have other acute, chronic, or exfoliative skin conditions (e.g., burns, impetigo, varicella zoster, severe acne, contact dermatitis, psoriasis, herpes or other open rashes or wounds), until the condition resolves.

- are pregnant or intend to become pregnant (due to the potential risk of fetal vaccinia); or are breast-feeding (due to the potential risk of contact transmission and inadvertent inoculation). It is currently unknown if vaccinia virus or antibodies are excreted in breast milk. Patients (*i.e.*, vaccinees) should avoid fathering a child for at least 4 months following completion of therapy with the recombinant vaccine.
- are in close contact with children less than 3 years of age (due to the potential risk of contact transmission and inadvertent inoculation).
- are immunodeficient or immunocompromised (by disease or therapy), including individuals with HIV infection.

Additionally, do not administer the recombinant vaccinia vaccine if the vaccinee:

- has a moderate or severe acute illness, until the illness resolves.
- is undergoing topical steroid therapy for inflammatory eye diseases, or undergoing therapy with systemic steroids; potential immune suppression increases risk for vaccinia-related complications.
- At this time, until a more definitive causal relationship is determined, it is recommended that patients with known CHF or clinically significant cardiomyopathy, not be vaccinated with recombinant vaccinia-based vaccines, due to the potential for development of myocarditis and/or pericarditis.

Although the CDC believes that there is no evidence to conclude that the licensed vaccinia vaccine used in the Smallpox Vaccination Program causes angina or heart attacks, it acknowledges a possible causal relationship between the vaccination and heart inflammation. The CDC continues to study the relationship, but in the meantime, recommends excluding individuals with underlying heart disease from participation in the current Smallpox Vaccination Program. Patients are being immunized with recombinant vaccinia vaccines with therapeutic intent and will be evaluated for cardiovascular risk factors and recent or symptomatic cardiac events per protocol eligibility criteria. Patients will be encouraged to minimize cardiovascular disease risks and encouraged to follow risk reduction according to standard medical practice.

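### Exclusion 2.1.2.12 and section 11.2.6 disagree on which contacts bar vaccinia vaccination, so a man can be randomised and then fall under an instruction not to vaccinate him

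*Combined protocol and SAP*

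**What the plan says.** **Eligibility, contacts (2.1.2.12).** A man is excluded if he is "Unable to avoid close contact or household contact with the following high-risk individuals for three weeks after the Day 1 vaccination". The groups are:
- children up to and including age 3, and women who are pregnant or nursing (after a less-than-or-equal sign, the text reads "3 years of age, (b) pregnant or nursing women");
- as the only item on skin disease, "c) individuals with prior or concurrent extensive eczema or other eczemoid skin disorders";
- as the item on immune status, "d) immunocompromised individuals, such as those with HIV".

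**Eligibility, the patient's own skin (2.1.2.10).** "History of atopic dermatitis or active skin condition (acute, chronic, exfoliative) that disrupts the epidermis".

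**Product section (11.2.6, Patient Care Implications and Contraindications).** The instruction opens "Do not administer the recombinant vaccinia vaccine if the recipient, or for at least three weeks after vaccination, their close household contacts" and lists the conditions that apply:
- on eczema, "have active eczema or a history of eczema or atopic dermatitis"; this item also names Darier's disease;
- on other skin disease, "have other acute, chronic, or exfoliative skin conditions (e.g., burns, impetigo, varicella zoster, severe acne, contact dermatitis, psoriasis"; the examples go on to include herpes and open wounds, and the bar lasts until the condition clears;
- pregnancy, intended pregnancy or breast-feeding;
- close contact with a child under 3;
- immune deficiency or compromise.

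It defines close household contacts as people who share housing or have close physical contact. That is in effect the same circle as in 2.1.2.12.

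**Registration (2.3 and 2.3.2).** Registration uses an eligibility checklist, and randomisation is completed 15 to 30 minutes after the checklist is sent.

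**The concern.** Both texts are current, and both address who may be exposed to live virus through the patient. They give different answers for the same household. A site screening against 2.1.2 has no reason to ask about a partner's limited past eczema or active psoriasis. The site preparing the dose under 11.2.6 does.

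The protocol's own account explains why this matters. Section 11.2 describes vaccinia as replication-competent in mammalian cells. Section 11.2.6 says that eczema vaccinatum can occur in eczematous contacts of vaccinated people, and on skin that was eczematous only in the past; it does not confine the risk to extensive disease. It gives a fatality rate of 30-40% untreated and about 7% once VIG was available. The people at risk are not trial participants.

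There is also a small consequence for the trial's conduct. A man randomised to Arm A and then barred at his first dose is randomised but unvaccinated, whereas his counterpart in Arm B can still supply a surveillance growth rate. Section 8 bases its sample size on evaluable patients with a growth-rate value from 0 to 6 months and does not say how such a man would be handled.

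**Working it through.** The protocol states no figure to reproduce for this point. The check is an item-by-item comparison, followed by a search for any other criterion that closes a gap.

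| Item | Eligibility (2.1.2) | Product section (11.2.6) | Result |
|---|---|---|---|
| Contact: eczema | Prior or concurrent, extensive; other eczemoid disorders | Any active or past eczema or atopic dermatitis | 2.1.2.12 narrower |
| Contact: Darier's disease | Not named | Named | 2.1.2.12 narrower |
| Contact: other skin conditions | None listed | Burns, impetigo, zoster, severe acne, psoriasis, herpes, open wounds and others, until resolved | 2.1.2.12 narrower |
| Contact: child | 3 years or under | Under 3 years | 2.1.2.12 slightly wider |
| Contact: pregnant or nursing | Listed | Listed | Same |
| Contact: intends pregnancy | Not listed | Listed | Largely covered for a partner by 2.1.1.16 |
| Contact: immunocompromised | Listed | Listed | Same |
| Recipient: own skin | History of atopic dermatitis; active epidermis-disrupting condition | Also any past eczema, and Darier's disease | Small residual gap |

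**Is a gap closed elsewhere?** Criterion 2.1.2.10 concerns the patient only. No other inclusion or exclusion criterion mentions a contact's skin.

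**Worked example.** A man's partner has active psoriasis.
1. Under 2.1.2.12, psoriasis is neither extensive eczema nor named, so he is not excluded on that ground.
2. Under 2.1.2.10, his own skin is clear, so he is not excluded.
3. If he meets the other criteria, he is registered and randomised.
4. Under 11.2.6, psoriasis in a close household contact is on the list, so the instruction is not to administer until it resolves.

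The opposite mismatch arises for a child aged exactly 3: covered by 2.1.2.12, but not by the age item in 11.2.6.

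**Expected transmissions.** Inputs are the contact-transmission rate in 11.2.6 (27 infections per million vaccinations, 1968 ten-state survey) and the accrual ceiling in section 8 (110).

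Expected number = rate × vaccinated men = (27 / 1,000,000) × 110 = 0.00297, or about 0.003.

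With the 72 evaluable men planned, (27 / 1,000,000) × 72 = 0.0019. Both figures apply the survey rate to this trial without adjustment. The survey concerned smallpox vaccination; this trial injects subcutaneously, a route for which 11.2.6 expects milder local reactions.

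**The case against.** The strongest reply is that 11.2.6 belongs to the same protocol and operates at dosing. An eligibility list followed by a stricter bar at administration can be seen as two layers of protection, and a site following both would withhold the vaccine. This stands. A reader might infer that the protocol allows men with such households to be vaccinated; the documents do not support that, because 11.2.6 forbids it in terms. What remains is that eligibility and the product section define the same hazard differently, so the conflict surfaces only after randomisation.

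Four further replies limit the point:
- **Pregnancy.** A reader might count a partner's intended pregnancy as an open gap. Criterion 2.1.1.16 requires contraception before entry, throughout therapy and for at least a month afterwards, and section 7.4.1.1 tells patients not to father a child. At most, other women in the household remain.
- **Recipient.** Criterion 2.1.2.10 is close to 11.2.6. What is left is past non-atopic eczema, and Darier's disease that is not active and disrupting the epidermis.
- **Narrower throughout.** This would be wrong: 2.1.2.12 is the wider rule on child age.
- **Wording.** The word extensive may not govern other eczemoid disorders, and the condition of being unable to avoid contact can be read alongside the three-week window in 11.2.6. Neither reading brings burns, impetigo, zoster, psoriasis or herpes in a contact within 2.1.2.12.

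The checklist form and the Appendix B patient instruction sheet were not available for this review. Either could repeat one list or the other, but neither would change the wording of 2.1.2.

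**Conclusion.** The point holds as an internal contradiction. Section 2.1.2.12 and section 11.2.6 disagree on contacts' skin conditions and on the child age limit, with a thin residual difference for the recipient between 2.1.2.10 and 11.2.6. A man can pass 2.1.2, be randomised, and then be barred from the vaccine.

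The risk in numbers is very small: about 0.003 expected transmissions at the ceiling of 110, assuming that the historical rate carries over. How many men would be classified differently depends on how many have such a contact, which the documents do not give, so no count is offered. The discrepancy does not alter the planned test for the primary endpoint. It merits correction because the harm described is severe, would fall on third parties, and is cheap to guard against with consistent wording.

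**What to change.** Reconcile 2.1.2.10 and 2.1.2.12 with 11.2.6 so that eligibility and the product section use one consistent list of recipient and contact conditions and one child age limit. Carry that list into the eligibility checklist. Which wording stands is for the sponsor to decide; this review takes no position on the clinical rule.

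The cost is an amendment to the wording and a checklist update. Depending on the wording chosen, a few men may be deferred or excluded at screening.
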